- a. To compare appendicular lean body mass and body composition versus placebo, and specifically ALM.
- b. To compare muscle strength using the knee extension test and the stair climb power test (SCPT) versus placebo.
- c. To compare the rate of successful patients who completed the 400MW test after the 6-month treatment versus placebo.
- d. To assess the overall score change on the SPPB as a cumulative expression of a physically frail status.
- e. To compare the repeated chair stand test as a sub-score of the SPPB assessment versus placebo.
- f. To compare the distance walked during the 6MWT versus placebo.
- g. To compare the change from the baseline using the SarQol autoevaluation questionnaire versus placebo.

Endpoints:

Primary Endpoint:

Gait speed measured during the 400MW test: the change from baseline to month 6 will be compared between groups of treatment (each dose versus placebo).

Key Secondary Endpoints:

PF-10 sub-score of the SF-36: the change from baseline to month 6 will be compared between groups of treatment (each dose versus placebo). Muscle strength as measured by the handgrip test: the change from baseline to month 6 will be compared between groups of treatment (each dose versus placebo). Additionally, a responder analysis will be performed with a responder definition of "study participant with an improvement of gait speed at 400MW test greater or equal to 0.1 m/s versus baseline", at an individual level.

A further responder analysis will be performed with a responder definition of "study participant with an improvement of PF10 greater or equal to 2 points versus baseline", at an individual level.

Other secondary Endpoints:

Change from baseline of ALM and other parameters of body composition by DEXA; the rate of success to complete 400MW test after a 6-month treatment versus placebo; change from baseline of muscle strength as measured by knee extension and SCPT; change from baseline of the total SPPB score and of the sub-score of the repeated chair stands test; change from baseline of the SarQol auto-evaluation questionnaire.

Study Population:

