		difference between the treatment groups and hence 0.1 m/s was chosen as the minimal clinically meaningful change for this study. A change of 0.1 m/sec will also be considered as a substantial clinically meaningful change to patients ³⁶ , and will be used for (individual) responders analysis.
Key Secondary:		
 To evaluate the effect of BIO101 on physical function from the study participants' perspective using an adapted PRO. To evaluate the effect of BIO101 on muscle strength using the handgrip strength test. 	 The PF-10 sub-score of the SF-36: the change from baseline to month 6/month 9 will be compared between groups of treatment (each dose versus placebo). Additionally, a responder analysis will be performed with a responder definition of "patient with an improvement of PF10 greater or equal to 2 points versus baseline", at an individual level. Handgrip strength test: the change from baseline to month 6/month 9 will be compared between groups of treatment, each dose versus placebo; a minimal clinically significant benefit is set at 2 kg of difference between groups. 	The SF-36 is a validated measure of health-related quality of life, sensitive to significant treatment effects, addressing health concepts that are relevant to the patients' perspectives. Specifically, the PF-10 has been used in numerous clinical trials and is considered a simple yet effective measure of mobility disability and also for epidemiological studies ³⁶ . Climbing one flight of stairs (no change versus decline of two levels, two-point difference) or walking a block (no change versus two levels decline) exemplifies a substantial meaningful change, as appreciated by patients ³⁶ . Change in muscle strength is directly related to the expected mechanism of action of the investigational drug and needs to be assessed. Assessment of muscle strength using the handgrip strength test is commonly used in interventional studies targeting muscle loss in older adults ^{21,23}
Other secondary		

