9.4.3 ANALYSIS OF THE SECONDARY ENDPOINT(S)

The key secondary endpoints (handgrip strength and PF-10 sub-score of the SF-36) will be analyzed with the same strategy as the primary endpoint (i.e. using a repeated measures mixed model to estimate the contrast at M6 of the difference of each active group versus placebo).

Missing data will not be replaced in these analyses but the MMRM model on observed data is known to perform well under a MAR hypothesis.

Additional sensitivity analyses may be added in the SAP during the blind-review meeting if the number of missing data is important (more than 10%).

Concerning the responder endpoints:

- 1. for the PF-10 sub-score of the SF-36, a responder analysis will be performed with a responder definition of "patient with an improvement of PF-10 greater or equal to 2 points versus baseline", at an individual level.
- 2. for the handgrip strength test: a responder definition is equal to the minimal significant benefit set at least 2 kg of improvement versus baseline, at an individual level.

The rate of responders (according to the predefined definitions provided in the corresponding endpoint sections) will be provided in each group of treatment at M3 and M6 visits for the PF-10 sub-score and at the M6 visit only for the handgrip strength test. Participants without any assessment for a parameter at a visit will be considered as non-responder for the corresponding parameter.

A logistic regression model with treatment group, gender and center as fixed effects will be used to compare each active group versus placebo at M6. The odds-ratio comparing groups will be provided as well as its 95% confidence interval. The multiplicity issue due to the two doses of active treatment will be addressed using the Hochberg procedure.

The other secondary and exploratory endpoints will be analyzed only in the FAS population.

Details and exploratory endpoints analyses will be provided in the SAP.

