Appendix C

Details of how to deal with missing data are also mentioned.

Standardized sub-scale scores will be presented to one decimal place. Handling of missing data and outliers.

Missing data will not be imputed in the primary analysis of the primary efficacy endpoint. No imputation for missing data will be used for the descriptive statistics and listings. Imputation for missing SF-36 sub-scale score data is detailed in Appendix B - Short Physical Performance Battery (SPPB)

Summary performance score: Each of the three performance measured is assigned a score ranging from 0 to 4, with 4 indicating the highest level of performance and 0 the inability to complete the test. For the test of balance, participants are assigned a score of 1 if they can hold a side-by-side standing position for 10 seconds but are unable to hold a semi-tandem position for 10 seconds; a score of 2 is assigned if they can hold a semi-tandem position for 10 seconds; a full-tandem position for 3 seconds; a score of 3 is assigned if they can stand in a full-tandem position for 3 seconds; a score of 4 is assigned if they can stand in a full tandem position for 10 seconds.

Four categories are computed for walking speed and chair stands, according to cut-off points that are based on quartiles of the time to perform each task assessed in the EPESE. The time of the faster of two walks is scored as follows: > 8.7 sec = 1; 6.21 to 8.70 sec = 2; 4.82 to 6.20 sec = 3; < 4.82 sec = 4; a score of 0 is assigned to participants unable to perform the test. The time required to perform five chair stands is scored as follows: $\ge 16.70 \text{ sec} = 1$; 13.70 to 16.69 sec = 2; 11.20 to 13.69 sec = 3; $\le 11.19 = 4$. A score of 0 is assigned to participants unable to perform the task. A summary score ranging from 0 (worst performers) to 12 (best performers) is calculated by adding subscores from the walking speed, chair stands and balance tests.

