Appendix C.

The handgrip strength test will be performed at Day 0 and at the M6/M9 visit or the end-ofintervention visit and will be measured 3 times for both hands. Grip strength is considered as the dominant hand so the highest of all 3 attempts for the dominant hand will be used for the analysis. The highest value for each hand will be summarized by treatment group. If there has been current flare-up of pain or has undergone fusion, arthroplasty, tendon repair, synovectomy, or other related surgery for the dominant hand or wrist in the past 3 months, the other hand will be tested. For the handgrip strength test, a minimum clinically significant benefit is set at 2 kg difference in the change at M6/M9 from baseline versus placebo in the mean difference between treatment groups.

Fatigue strength will be summarized by treatment group.

The analysis of change from baseline to M6/M9 in Physical Function Domain (PF-10) will use the same method as for analysis of the primary efficacy endpoint as detailed in section 8.7.1.1.

Missing data will not be replaced in these analyses but the MMRM model on observed data is known to perform well under a MAR hypothesis.

An ANCOVA method detailed in section 8.7.1.12 will be used to analyse change from baseline to M6/M9 in Handgrip strength test.

Alternative methods to adjudicate missing data for the primary endpoint like the Bayesian Multiple Imputation (MI) methods will also be considered for Physical Function Domain (PF-10). Chen at al (2017) demonstrated the interest of applying Bayesian MI method to 400MW non-completers in the LIFE study⁹. More detail please refer to section 8.7.6.

A responder analysis will be performed, using a logistic regression (method defined in section 8.7.1.33) to model PF-10 response at M6/M9. A responder is defined as an improvement of PF-10 greater or equal to 2 points compared to the baseline value, at an individual level. A non-responder for a visit (M3 or M6/M9) will be defined as a subject that is not a responder at that visit. Subjects with a missing value at a visit (M3 or M6/M9) will be considered as non-responders. The number and rate (%) of responders and non-responders will be provided by treatment group for the M3 and M6/M9 visits.

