8.7.5 Analysis of other efficacy datas

All other efficacy data described here will be summarized using the FAS.

Descriptive statistics of the observed scores and change from baseline by treatment group for each scheduled visit will be provided.

- Time to walk 400m, 200m, 100m
- SF-36: 8 subscales and two summary scores. The 8 subscales are: physical functioning, role limitations due to physical problems, bodily pain, general health perceptions, vitality, social functioning, role-limitations due to emotional problems, and mental health. The two summary scores are the physical component summary and the mental component summary. Each scale is directly transformed into a 0-100 scale on the assumption that each question carries equal weight. The lower the score, the more disability; the higher the score the, less disability (i.e., a score of zero is equivalent to maximum disability and a score of 100 is equivalent to no disability).

By-subject listings of other efficacy data will also be provided.

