Description of item	Lowest possible score	Range of Sub-scale score
PF-10	10	20
Role limitations due to-physical problems	4	16
Bodily Pain	2	10
General Health perceptions	5	20
Vitality	4	16
Mental Health	5	20
Role-limitations due to emotional problems	3	12
Social Functioning	2	8

The following is an example of the SAS® code used to divide the 36 questions (recoded as necessary) into the 8 sub-classifications and to transform the values to a 0 - 100 scale.

data SF36;

```
tot_PF=sum(of Q3A Q3B Q3C Q3D Q3E Q3F Q3G Q3H Q3I Q3J);
tot_RP=sum(of Q4A Q4B Q4C Q4D);
tot_BP=sum(of Q7 Q8);
tot_GH=sum(of Q1 Q11A Q11B Q11C Q11D);
tot_VT=sum(of Q9A Q9E Q9G Q9I);
tot_SF=sum(of Q6 Q10);
tot_RE=sum(of Q5A Q5B Q5C);
tot_MH=sum(of Q9B Q9C Q9D Q9F Q9H);
sf36_PF=((tot_PF - 10)/(20))*100;
sf36_BP=((tot_PF - 4)/(16))*100;
sf36_GH=((tot_BP - 2)/(10))*100;
sf36_SF=((tot_GH - 5)/(20))*100;
sf36_SF=((tot_SF - 2)/(8))*100;
```

Version Final 2.0, Date: 04JUN2021

Page 54 of 69

```
sf36_RE=((tot_RE - 3)/(12))*100;
sf36_MH=((tot_MH - 5)/(20))*100;
label sf36_PF = "Physical functioning score (10 items)"
sf36_RP = "Role-physical score (4 items)"
sf36_BP = "Bodily pain (2 items)"
sf36_GH = "General health score (5 items)"
sf36_VT = "Vitality score (4 items)"
sf36_SF = "Social functioning score (2 items)"
sf36_RE = "Role-emotional score (3 items)"
sf36_MH = "Mental health score (5 items)"
;
```

run;

Two summary measures of physical and mental health are constructed from the eight sub-scales, If any item in the calculation is missing, then the summary measure score is missing:

- Physical Health = $(sf36_PF + sf36_RP + sf36_BP + sf36_GH) / 4$
- Mental Health = $(sf36_VT + sf36_SF + sf36_RE + sf36_MH) / 4$

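### On the SAP's 0–100 PF-10 score, which moves in steps of 5 when all items are answered, the 2-point responder cut-off is met by any net improvement if the same number of items is answered at both visits; it agrees with the protocol's own example only on the raw sum

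*SAP*

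**What the plan says.** **Responder rule.** SAP 8.7.3.1: "A responder is defined as an improvement of PF-10 greater or equal to 2 points compared to the baseline value, at an individual level". The protocol has the same rule in section 1.1 ("study participant with an improvement of PF10 greater or equal to 2 points versus baseline"), in the endpoint table of section 3, and in section 9.4.3 ("patient with an improvement of PF-10 greater or equal to 2 points versus baseline"). None of these places names a unit. On missing scores, SAP 8.7.3.1 says: "Subjects with a missing value at a visit (M3 or M6/M9) will be considered as non-responders".

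**Scoring.** SAP 8.7.3.1 sends the reader to Appendix C for the PF-10 calculation. Appendix C gives a lowest raw score of 10 and a range of 20, and codes "sf36_PF=((tot_PF - 10)/(20))*100". SAP 8.7.5 says of the SF-36 scales: "Each scale is directly transformed into a 0-100 scale on the assumption that each question carries equal weight". Protocol 8.1 says the same, and SAP 7.1.2.1 adds: "Standardized sub-scale scores will be presented to one decimal place". No text says that the raw sum is analysed. If fewer than half the items are missing, Appendix C fills them with the participant's own mean.

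**Example.** In the same table row of Protocol section 3 as the definition, the justification reads "Climbing one flight of stairs (no change versus decline of two levels, two-point difference" and treats this as a substantial change. The example recurs as PF-10 background in Protocol 2.2, 4.2 and 8.1. It does not appear in SAP 8.7.3.1.

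**Group-level benefit.** Protocol 1.1 sets the minimum benefit for PF-10 between groups at 2 points, also without a unit.

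**The concern.** A responder cut-off is meant to separate a change worth counting from a smaller one. If it lies below the resolution of the score, it separates nothing: one level gained on one item, with no other change, makes a responder. The nearby protocol text speaks of a substantial change for patients, so a responder rate computed this way could be taken for more than it is.

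The responder comparison is also formal. Protocol 9.4.3 and SAP 8.7.1.3 plan a logistic regression with odds ratios for each dose against placebo, and Hochberg adjustment for the two doses. If the unit is left open until results are known, two different rates could each be defended from the documents.

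**Working it through.** **Inputs.** Ten PF-10 items (SAP 7.1.2.1); lowest raw score 10, range 20 and the 0–100 formula (SAP Appendix C); cut-off 2 points (SAP 8.7.3.1). The documents do not list the item levels. Ten equally weighted items with lowest sum 10 and range 20 imply levels 1 to 3.

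**1. The plan's own figures.** Lowest sum 10 × 1 = 10; highest 10 × 3 = 30; range 20. Score = (raw − 10)/20 × 100 runs from 0 to 100. This reproduces Appendix C.

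**2. Size of a step.** 100/20 = 5 points per raw level. Two points on 0–100 are 2 × 20/100 = 0.4 of a level; two raw levels are 2 × 5 = 10 points.

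**3. What the cut-off selects, complete items.** There are 21 × 21 = 441 pairs of baseline and follow-up sums. A gain of at least 2 points on 0–100 coincides with any net gain in all 441. Any cut-off above 0 and up to 5 gives the same rule. The 0–100 and raw readings disagree in 20 pairs, exactly those where the raw sum rises by 1.

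**4. Missing items.** With person-mean filling, score = 50 × (mean item level − 1). If 10, 9, 8, 7 or 6 items are answered at both visits, the smallest positive change is 50/10 = 5.0, 50/9 = 5.6, 50/8 = 6.3, 50/7 = 7.1 or 50/6 = 8.3, so step 3 still holds. If the numbers differ it can fail: with 9 items at one visit and 10 at the other, the smallest positive change is 50/90 = 0.56, which is an improvement but not a response.

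**5. Effect on rates (illustration only).** The documents give no mean or SD for PF-10 change. Assume a normal raw change with continuity correction, SD 2, 3 or 4 levels (10, 15 or 20 points), and everyone observed. Then P(gain ≥ 1 level) = 1 − Φ((0.5 − mean)/SD) and P(gain ≥ 2 levels) = 1 − Φ((1.5 − mean)/SD). Responders in percent, 0–100 reading / raw reading:

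| SD (points) | mean −5 | mean 0 | mean +5 |
|---|---|---|---|
| 10 | 22.7 / 10.6 | 40.1 / 22.7 | 59.9 / 40.1 |
| 15 | 30.9 / 20.2 | 43.4 / 30.9 | 56.6 / 43.4 |
| 20 | 35.4 / 26.6 | 45.0 / 35.4 | 55.0 / 45.0 |

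Before rounding, the gap runs from 8.8 to 19.7 percentage points. If 20% of scores were missing and counted as non-response, the zero-mean rates are multiplied by 0.8: 32.1, 34.7 and 36.0 against 18.1, 24.7 and 28.3. The 20% is borrowed from the withdrawal allowance in Protocol 9.2; questionnaires continued by telephone, so it may not fit PF-10.

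**6. Effect on the treatment comparison.** For a mean of +5 points in one arm against 0 in the other, the odds ratios from unrounded probabilities are 2.23, 1.70 and 1.49 on the 0–100 reading and 2.29, 1.72 and 1.50 on the raw reading.

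**The case against.** **The scale is not really open.** The responder sentence has no unit, but its section refers to Appendix C, which has one formula. A programmer can run the rule and get one answer. This stands, and a reader who infers that the SAP cannot be executed goes too far. It does not remove the problem: that one answer is a cut-off finer than the score.

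**The example may be irrelevant.** It describes a two-level decline on a single item, whereas the responder rule concerns improvement in a ten-item score. For gait speed, Protocol section 3 says outright that the substantial change serves the individual responder analysis; there is no such sentence for PF-10. The figure may simply reuse the 2-point between-group benefit of Protocol 1.1, as Protocol 9.4.3 does openly for handgrip with 2 kg. This also stands. It means the example cannot show what was intended. A figure carried over from a difference in group means would still need checking against the step size of an individual score.

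**Little depends on it.** The analysis is additional, the odds ratios hardly move in the illustration, and the responder definitions never themselves call a PF-10 responder meaningfully improved. All true, and it limits the point to the rate and how it is described.

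**Conclusion.** The concern holds in a limited form. Under the SAP's own scoring, the 2-point cut-off does no work beyond identifying a net improvement, provided the same number of items is answered at both visits. That part is arithmetic and needs no assumption about the data. The cut-off agrees with the protocol's two-level example only on the raw 10–30 sum. The size in responder rates, about 9 to 20 percentage points, rests on the assumed means, SDs and normal model, with no missing scores.

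Three stronger readings are not supported:

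- A reader might infer that 10 points on 0–100 was the intended cut-off and that the SAP misapplies it. No text derives the cut-off from the example, so the mismatch is unexplained but is not a proven error.
- A reader might take the equivalence with any improvement as unconditional. The missing-item rule breaks it when the number of answered items differs between visits.
- A reader might conclude that the treatment comparison is distorted. Under a pure mean shift the odds ratios are nearly the same, and validity under the null, the PF-10 mixed model, the primary endpoint and the sample size do not depend on this cut-off.

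It should be corrected because the remedy is cheap and the responder analysis is a planned comparison on a key secondary measure.

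**What to change.** Before unblinding, reconcile the cut-off with the scoring in one of two ways:

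- define a responder as a gain of at least 2 on the raw 10–30 sum, equal to at least 10 on 0–100, and give the justification, since the example alone does not supply one; or
- keep 2 points on the 0–100 score and report the result as *any net improvement*, not as a meaningful change. Add a note that small gains can miss the cut-off when the number of answered items differs between visits.

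At the same time, name the unit of the 2-point between-group benefit in Protocol 1.1.

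The cost is wording in SAP 8.7.3.1 and Protocol 1.1, 3 and 9.4.3, plus one derivation line. No new data are needed. If the raw-sum cut-off is chosen, responder rates will be lower in all arms.

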8.7.3.2 Analysis of other secondary efficacy endpoints

The other secondary endpoints will be analyzed using the FAS only.

Observed and change from baseline values for the following secondary efficacy endpoints will be summarized using descriptive statistics by treatment group. These endpoints will be analyzed using an ANCOVA method as defined in Section 8.7.1.12. This analysis will be performed without any correction for multiplicity.

- Change from baseline in ALM and other parameters of body composition by DEXA: The DEXA parameters will be ALM, ALM BMI, percentage lean mass for left/right arm, trunk and left/right leg and percentage fat mass for trunk, right/left leg and right/left arms.
- Change from baseline in muscle strength (knee extension) and stair climb power test (SCPT):

Knee extension will be performed at Day 0 and at the M6/M9 visit or the end-of-intervention visit and is measured using the maximum peak torque measurement (Nm) for 60°/s, 90°/s and 180°/s for the tested leg (either right or left). It is usually measured as the force applied to the ankle with the subject seated in an adjustable straight-back chair, the lower leg unsupported and the knee flexed to 90°. Knee extension will be measured 3 times for the chosen leg. The highest of all 3 attempts will be used for the summary and analysis. The assay with the highest torque output (highest value) will be taken for analyses.

The SCPT will be performed at Day 0 and at the M6/M9 visit and is the measure of ability to ascend and descend stairs which tests the body strength and balance. SCPT measures the time (in seconds) taken to ascend and descend a flight of stairs (10 steps with a 20cm step height). Step heights should be suitable (between 16 and 20 cm).

• Change from baseline in Pepper Assessment Tool for Disability (PAT-D) for obese patient.

The PAT-D is a disability questionnaire that was developed to assess difficulty with functioning in both discrete tasks and social/role functioning. There are three domains: mobility, activities of daily living, and instrumental activities of daily living. This questionnaire asks respondents how much difficulty they have had with a range of activities in the past month due to their health. For each item, respondents answer on a 5-point Likert-type scale whether they experience: (1) no difficulty, (2) a little difficulty, (3) some difficulty, (4) a lot of difficulty, or (5) unable to do. For each item there is also a 'not applicable' option if the respondent usually did not do that activity for reasons other than disability. The PAT-D produces a score for each of the three domains (basic ADLs, mobility and IADLs) as well as a total score, with higher scores indicating greater disability. See Appendix D for method of calculation. The PAT-D will be performed at Day 0 and at the M6/M9 visit.

• Change from baseline to month 6 (M6)/month 9 (M9) in 6MWT distance The 6MWT is a test for functional exercise capacity and involves measuring the distance a participant can cover within the allotted time of 6 minutes. The 6MWT will be performed at Day 0 and at the M6/M9 visit.

The following secondary efficacy endpoints will be summarized using descriptive statistics by treatment group and analyzed using a MMRM analysis as defined in Section 8.7.1.11. This analysis will be performed without any correction for multiplicity.

- Change from baseline in the Short Physical Performance Battery (SPPB) total score: The SPPB is evaluated at Screening, M3 and M6/M9 or end of study visit and is a brief performance battery based on timed short distance walk, repeated chair stands and balance test. Change from baseline of SPPB will provide an estimate of the overall clinical impact of treatment on the burden of physical frailty. The Screening value will be considered to be the baseline value. If the screening value is missing the baseline value will be considered as missing. The scores for the individual tests and the total SPPB score are recorded in the CRF. Total gait speed test score, total chair stand test score, total balance test score and total SPPB score will be summarized by visit for each treatment group.
- Change from baseline of the time for five chair stands as part of the SPPB assessment. Time will be in seconds. The Screening value will be considered to be the baseline value. If the screening value is missing the baseline value will be considered as missing. The total time to five chair stands will be summarized by visit for each treatment group.

• Change from baseline in SarQol auto evaluation questionnaire:

SarQol sarcopenia-specific is evaluated at Screening, M3 and M6/M9 or end of study visit and is self-administered, quality of life questionnaire, designed for community-dwelling elderly subjects aged 65 years and older.

The questionnaire contains 22 questions, which covers 7 domains: physical and mental health; locomotion; body composition; functionality; activities of daily living; leisure activities; and fears. Most questions are answered on a 4 point or 5-point Likert scale. The total and domain score for the SarQol will be summarized by visit for each treatment group.

• Change from baseline in TSD-OC for obese patient

The TSD-OC is considered a reliable and valid instrument for measuring self-reported disability in obese subjects. The questionnaire is a set of multiple questions in 7 dimensions to measure pain; stiffness; function and autonomy in daily activities, housework, outdoor activities, occupational activities, and social life. Each question is scored by the subject from 0 (best) to 10 (worst). Each dimension score is calculated and then all dimension scores are added together for a total TSD-OC score. The TSD-OC will be performed at Day 0, M3 and

M6/M9 or End of intervention Visit. The total score will be summarized by visit for each treatment group.

The 400MW test is a dichotomous test, failure being defined as the inability to walk 400 meters in 15 minutes without needing to sit or require help. The number and percentage of success and failure to complete the 400 MW test at M6/M9 will be presented by treatment group.

The rate of success to complete the 400 meter walking (400 MW) test after 6/9 months of treatment will be analyzed using the Cochran Mantel-Haenszel (CMH) test adjusted for center and gender per Section 8.7.1.4.

A by-subject listing will be provided for secondary efficacy endpoint data.

Statistical Analysis Plan Protocol Number: BIO101-CL03 Version Final 2.0, Date: 04JUN2021

Page 39 of 69

